5.3.2 Pembrolizumab

Pembrolizumab will be administered by trained medical personnel at the investigational site. Treatment compliance will be monitored through documentation of study treatment administration in the participant's medical record.

Pembrolizumab will be administered in the outpatient clinic on Day 1 of each cycle. Pembrolizumab should be prepared and administered as an approximately 30-minute IV infusion per institutional standard, infuse prior to Eribulin

Please refer to the FDA-approved package insert for pembrolizumab for product information and a comprehensive list of adverse events. Pembrolizumab should be prepared and administered per institutional standard. Institutional standard procedures include BSA calculations, body weight assessments and dose calculations/recalculations. Infusion times may be prolonged in participants who experience an infusion reaction as per section 5.9.

Pembrolizumab should be administered prior to eribulin administration. There should be no overlap in timing of the two administrations.

The standard dose of pembrolizumab is 200mg IV.

5.3.3 *Discontinuation of eribulin*

If eribulin is stopped for toxicity, participants are permitted to continue protocol therapy with pembrolizumab alone.

5.3.4 *Discontinuation of pembrolizumab*

If pembrolizumab is stopped for toxicity, participants are permitted to continue protocol therapy with eribulin alone.

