5.5 Duration of Therapy

Duration of therapy will depend on individual response, evidence of disease progression and tolerance. In the absence of treatment delays due to adverse event(s), treatment may continue for 2 years or 35 cycles of therapy or until one of the following criteria applies:

- Disease progression in any participant who showed first radiologic evidence of progressive disease (PD) by RECIST 1.1 (see Section 11.1.4) and is deemed clinically stable, it is at the discretion of the investigator to continue treating the participant until progression is confirmed at least 4 weeks from the date of the first radiologic evidence of PD. Further details are described below.
- Intercurrent illness that prevents further administration of treatment
- Unacceptable adverse event(s) which include the following (see also section):
 - Any Grade 2 drug-related uveitis or eye pain or blurred vision that does not respond to topical therapy and does not improve to Grade 1 severity within the re-treatment period OR requires systemic treatment
 - Participants requiring > two dose delays for the same type of event should be removed from protocol
 - Any adverse event, laboratory abnormality, or intercurrent illness which, in the judgment of the investigator, presents a substantial clinical risk to the participant with continued study drug dosing
 - Any dosing interruption lasting >5 weeks, with the following exceptions:
 - Participants being tapered after high dose corticosteroids over one month followed by a two-week observation period will be allowed an additional two weeks to restart treatment (a maximum eight-week interruption).
 - Dosing interruptions >5 weeks that occur for non-drug-related reasons may be allowed if approved by the Investigator. Prior to re-initiating treatment in a participant with a dosing interruption lasting >5 weeks, the PI must be consulted.
 - Grade 2 pneumonitis requiring steroids.
 - Grade 3 or Grade 4 drug-related autoimmune or inflammatory events including uveitis, pneumonitis, diarrhea, colitis, neurologic adverse events, hypersensitivity reaction, or infusion reaction of any duration requires discontinuation except as noted below:
 - Any other grade 3 non-skin, drug-related AE lasting >7 days including fatigue.

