 - Any grade 3 or 4 drug-related laboratory abnormality or electrolyte abnormality, not associated with underlying organ pathology, that does not require treatment except for electrolyte replacements **does not** require treatment discontinuation.
 - Grade 3 amylase or lipase abnormalities that are not associated with diabetes mellitus (DM), associated liver or gall bladder inflammation clinical manifestations of pancreatitis and which decrease to < Grade 2

within 1 week of onset **may** resume study treatment when resolved.

- Any grade 4 events except as noted above.
- Any participants who require additional immune suppressive treatment beyond steroids should go off study treatment
- Participant demonstrates an inability or unwillingness to comply with the medication regimen and/or documentation requirements
- Participant decides to withdraw from the protocol therapy
- General or specific changes in the participant's condition render the participant unacceptable for further treatment in the judgment of the treating investigator

Participants will be removed from the protocol therapy when any of these criteria apply. The reason for removal from protocol therapy, and the date the participant was removed, must be documented in the case report form (CRF). Alternative care options will be discussed with the participant.

In the event of unusual or life-threatening complications, treating investigators must immediately notify the Overall PI, [name], MD.

Confirmation of Progressive Disease

Pembrolizumab, like other immunotherapeutic agents, may produce antitumor effects by potentiating endogenous cancer-specific immune responses. The response patterns seen with such an approach may extend beyond the typical time course of image responses seen with cytotoxic agents, and can manifest as a clinical response after an initial increase in tumor burden or even the appearance of new lesions.

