AST and ALT elevation or Increased bilirubin	Grade 2	Withhold	
 • Administer corticosteroids (initial dose of 0.5- 1 mg/kg prednisone or equivalent) followed by taper 	
 • Monitor with liver function tests (consider weekly or more frequently until liver enzyme value returned to baseline or is stable)

	Grade 3 or 4	Permanently discontinue	
 Administer corticosteroids (initial dose of 1-2 mg/kg prednisone or equivalent) followed by taper 	
Type 1 diabetes mellitus (T1DM) or Hyperglycemia	Newly onset T1DM or Grade 3 or 4 hyperglycemia associated with evidence of β -cell failure	Withhold	
 Initiate insulin replacement therapy for participants with T1DM Administer anti-hyperglycemic in participants with hyperglycemia 	
 Monitor participants for hyperglycemia or other signs and symptoms of diabetes.
Hypophysitis	Grade 2	Withhold	
 Administer corticosteroids and initiate hormonal replacements as clinically indicated. 	
 Monitor for signs and symptoms of hypophysitis (including hypopituitarism and adrenal insufficiency)
	Grade 3 or 4	Withhold or permanently discontinue ¹		
Hyperthyroidism	Grade 2	Continue	
 Treat with non-selective beta-blockers (eg, propranolol) or thionamides as appropriate 	
 Monitor for signs and symptoms of thyroid disorders.
	Grade 3 or 4	Withhold or permanently discontinue ¹		
Hypothyroidism	Grade 2-4	Continue	
 Initiate thyroid replacement hormones (eg, levothyroxine or liothyronine) per standard of care 	
 Monitor for signs and symptoms of thyroid disorders.
Nephritis and Renal dysfunction	Grade 2	Withhold	
 Administer corticosteroids (prednisone 1-2 mg/kg or equivalent) followed by taper. 	
 Monitor changes of renal function
	Grade 3 or 4	Permanently discontinue		
Myocarditis	Grade 1 or 2	Withhold	
 Based on severity of AE administer corticosteroids 	
 Ensure adequate evaluation to confirm etiology and/or exclude other causes
	Grade 3 or 4	Permanently discontinue		

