All other immune-related AEs	Intolerable/persistent Grade 2	Withhold	
 Based on type and severity of AE administer corticosteroids 	
 Ensure adequate evaluation to confirm etiology and/or exclude other causes
	Grade 3	Withhold or discontinue based on the type of event. Events that require discontinuation include and not limited to: Guillain-Barre Syndrome, encephalitis		

	Grade 4 or recurrent Grade 3	Permanently discontinue		
1. Withhold or permanently discontinue pembrolizumab is at the discretion of the investigator or treating physician. NOTE: For participants with Grade 3 or 4 immune-related endocrinopathy where withhold of pembrolizumab is required, pembrolizumab may be resumed when AE resolves to \leq Grade 2 and is controlled with hormonal replacement therapy or achieved metabolic control (in case of T1DM).				

Table 4.2 Pembrolizumab dose delay for non-immunologically mediated adverse events

ALL OTHER EVENTS*	Management/Next Dose for Pembrolizumab
\leq Grade 1	No change in dose
Grade 2	Hold until \leq Grade 1 OR baseline (exceptions as noted below); Evaluate and continue at investigator discretion
Grade 3	Stop pembrolizumab (exceptions as noted below)
Grade 4	Stop pembrolizumab
*Not Pembrolizumab related, or pembrolizumab related non-immunologically mediated Recommended management: As clinically indicated	

- Any grade 2 drug-related uveitis or eye pain or blurred vision that does not respond to topical therapy and does not improve to Grade 1 severity within the re-treatment period OR requires systemic treatment should result in protocol treatment discontinuation.
- Any adverse event, laboratory abnormality, or intercurrent illness which, in the judgment of the investigator, presents a substantial clinical risk to the participant with continued study drug dosing should result in protocol treatment discontinuation.
- Tumor pain or associated tumor flare does not require permanent discontinuation.
- Participants with any grade < 2 laboratory abnormality may continue study treatment at the discretion^[SEP] of the investigator. Any grade 3 or 4 drug-related laboratory abnormality or electrolyte abnormality, that can be managed independently from underlying organ pathology with electrolyte replacement, hormone replacement, insulin, or that does not require treatment **does not** require discontinuation.

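### Sections 5.5 and 6.2 give conflicting discontinuation rules for Grade 3-4 drug-related laboratory abnormalities managed with hormone replacement or insulin

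*Combined protocol and SAP*

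**What the plan says.** Section 5.5 lists the reasons for ending protocol therapy and closes with "Participants will be removed from the protocol therapy when any of these criteria apply". Three of its lines bear on this point:

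- For Grade 4: "Any grade 4 events except as noted above".
- For Grade 3: "Any other grade 3 non-skin, drug-related AE lasting >7 days including fatigue".
- For immune events of any duration, unless excepted: "Grade 3 or Grade 4 drug-related autoimmune or inflammatory events including uveitis, pneumonitis, diarrhea, colitis, neurologic adverse events, hypersensitivity reaction, or infusion reaction".

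The exception for laboratory and electrolyte abnormalities of Grade 3 or 4 is limited to those "not associated with underlying organ pathology, that does not require treatment except for electrolyte replacements".

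Section 6.2 repeats that exception in the bullets under Table 4.2 with a different scope. There it covers an abnormality "that can be managed independently from underlying organ pathology with electrolyte replacement, hormone replacement, insulin, or that does not require treatment".

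Table 4.1, also in 6.2, sets the pembrolizumab action for immune-related events. For hypothyroidism of Grade 2 to 4 the action is to continue, with the instruction "Initiate thyroid replacement hormones (eg, levothyroxine or liothyronine) per standard of care". For new type 1 diabetes, or Grade 3-4 hyperglycemia with evidence of beta-cell failure, the action is to withhold. A note to the table allows resumption after a withheld Grade 3 or 4 endocrinopathy once it is controlled and has come down to Grade 2 or less. Table 4.4 says that pembrolizumab stops if diabetes develops.

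On single-drug continuation, section 5.3.4 states: "If pembrolizumab is stopped for toxicity, participants are permitted to continue protocol therapy with eribulin alone". Section 5.8 and section 6 say much the same.

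**The concern.** Two sentences that appear to state one rule give opposite instructions for the same event. An investigator working from 5.5 would remove a participant whom an investigator working from 6.2 could keep on treatment. Events managed with hormones or insulin are recognized effects of pembrolizumab; the protocol's own expected-event list includes thyroid, pituitary and adrenal disorders and type 1 diabetes.

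Three things are at stake: consistent handling of participants, the treatment each one actually receives, and the removal reason entered on the case report form. There is also a possible route to the primary endpoint. Once off treatment without progression, a participant moves from scans every 6 weeks (11.1) to scans every 8 weeks where possible (5.6), and 13.1 scores a missing 12-week scan as a failure.

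**Working it through.** The main check is a comparison of rules. The plan states no figure to reproduce.

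| Drug-related event | Section 5.5 | Section 6.2 |
|---|---|---|
| Grade 4 laboratory abnormality managed with insulin or hormone replacement | Outside the exemption; removed under the Grade 4 line | Inside the Table 4.2 bullet; discontinuation not required |
| Grade 4 hypothyroidism on thyroid replacement | Removed under the Grade 4 line | Table 4.1: continue |
| Grade 3, same management, more than 7 days | Removed under the Grade 3 line | Inside the Table 4.2 bullet |
| Grade 3, classed as autoimmune or inflammatory, any duration | Removed under the immune-event line | Table 4.1: continue for hypothyroidism; withhold, with possible resumption, for diabetes or hyperglycemia with beta-cell failure |
| Grade 3, not autoimmune or inflammatory, 7 days or less | Not removed | Inside the Table 4.2 bullet; no conflict |

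The first four rows conflict and the last does not. The two exemptions also treat organ pathology differently: under 5.5 an association with it removes the exemption, while under 6.2 the test is whether the abnormality can be managed independently of it.

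No text gives one section precedence. The cross-reference attached to the unacceptable-adverse-event item in 5.5, which might have settled the matter, names no section.

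Other passages do not fit together either:

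- 5.5 removes the participant from protocol therapy, whereas 5.3.4, 5.8 and section 6 let eribulin continue alone.
- 5.8 lets Grade 3 thyroiditis continue, and lets stable thyroiditis or hypopituitarism restart on replacement hormones.
- Table 4.1 withholds pembrolizumab for new type 1 diabetes, and Table 4.4 stops it for diabetes.

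For size, section 2.6 gives Grade 3-4 rates in the breast cancer trial of the combination: hyperglycemia 1.9%, type I diabetes 1.9%, adrenal insufficiency 0.9%. The overlap between them is not given, so it is taken at both extremes:

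- Complete overlap: 57 × 0.019 = 1.1 participants, or 19 × 0.019 = 0.4 per arm.
- No overlap: 0.019 + 0.019 + 0.009 = 0.047; 57 × 0.047 = 2.7 participants, or 19 × 0.047 = 0.9 per arm.

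Grade 3-4 thyroid rates are not given (all grades: hypothyroidism 18.7%, hyperthyroidism 8.4%), so thyroid events are not counted here.

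**The case against.** The strongest reply is that the two sections are closer than a bare comparison of sentences suggests. Several parts of it stand.

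A reader might infer that the same laboratory value ends both drugs under 5.5 and neither under 6.2. The documents do not support that in general. The loss of both drugs follows from the removal sentence in 5.5, but 5.3.4 treats eribulin alone as continuing protocol therapy. Section 6.2 does not simply carry on either. Table 4.1 withholds pembrolizumab for new type 1 diabetes or hyperglycemia with beta-cell failure, and withholds or permanently discontinues it for Grade 3-4 hyperthyroidism. Table 4.4 stops it for diabetes.

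The wider exemption also sits under a table for events that are not immune-mediated, so it may not reach immune endocrine events. That narrows the reach of the bullet but does not remove the conflict, because the hypothyroidism row of the immune table also departs from the Grade 4 line of 5.5.

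The reading of 5.5 depends partly on list layout. The 7-day Grade 3 line comes directly after words that announce exceptions. The nesting should be checked in the source document.

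A reader might also turn the rates above into a chance of at least one case: 1 − 0.981^57 = 66% to 1 − 0.953^57 = 94%. That is the chance of any such Grade 3-4 event. It is not the chance that the rules collide. The rates are for immune-related events over all treatment and are not filtered for duration, management or timing. Diabetes and adrenal insufficiency are diagnoses, so not every case would be recorded as a laboratory abnormality.

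**Conclusion.** The contradiction is real and should be reconciled. It is unconditional at Grade 4 for abnormalities managed with insulin or hormone replacement, and for Grade 4 hypothyroidism. At Grade 3 it is limited to events lasting more than 7 days or classed as autoimmune or inflammatory.

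The scale is small: about 1 to 3 of 57 participants with one of the three listed events, assuming that the breast cancer rates carry over to sarcoma and leaving out thyroid events, for which no Grade 3-4 rate is given. Only some of these participants would meet the conflict.

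It is tempting to conclude that the 9-of-19 decision in an arm turns on which page is followed. That would need a qualifying event before week 12, removal, a missed 12-week scan, and a participant otherwise free of progression. The documents give no figure for that chain, so no effect on the primary result is shown. The firmer consequence is that treatment received and recorded removals could differ between participants with the same event. This review takes no position on which rule is clinically right.

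**What to change.** Reconcile section 5.5, section 5.8, the bullets under Table 4.2, the endocrine rows and note of Table 4.1, and the diabetes wording of Table 4.4. Use one identical exemption sentence in 5.5 and 6.2 that states:

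- which managed abnormalities are exempt;
- whether an association with organ pathology removes the exemption;
- whether the consequence applies to pembrolizumab only or to all protocol therapy, consistently with 5.3.4, 5.8 and section 6.

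Complete the open cross-reference in 5.5, and make the nesting of its list unambiguous so that removal lines and exceptions can be told apart. The clinical team decides the content. The cost is amendment wording only, with no added procedures or participants.

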6. DOSING DELAYS/DOSE MODIFICATIONS

Dose delays and modifications will be made as indicated in the following table(s). The descriptions and grading scales found in the revised NCI Common Terminology Criteria for Adverse Events (CTCAE) version 5.0 will be utilized for dose delays and dose modifications. A copy of the CTCAE version 5.0 can be downloaded from the CTEP website http://ctep.cancer.gov/protocolDevelopment/electronic_applications/ctc.htm.

Dosing interruptions are permitted in the case of medical / surgical events or logistical reasons not related to study therapy (e.g., elective surgery, unrelated medical events, participant vacation, and/or holidays). Participants should be placed back on study therapy within 5 weeks of the scheduled interruption, unless otherwise discussed with the Sponsor. The reason for interruption should be documented in the participant's study record.

Dose modifications and delays for eribulin will be allowed and are described below. No re-escalation will be allowed for eribulin. Dose delays for pembrolizumab for adverse events are described below. There are no dose reductions of pembrolizumab allowed. See Section 5.9 for guidelines regarding resumption of pembrolizumab following dose delays.

For toxicities in this Section which are attributable to pembrolizumab alone, only pembrolizumab should be held as directed. It is permissible to continue eribulin despite discontinuation of pembrolizumab in these select cases. This will be left to the treating physician's discretion after discussion and approval of the study PI.

For toxicities in this Section which are attributable to eribulin alone, only eribulin should be held

as directed. It is permissible to continue pembrolizumab despite discontinuation of eribulin in these select cases. This will be left to the treating physician's discretion after discussion and approval by the study PI.

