Grade 4	Hold eribulin until recovery to grade < 2 then reduce by 1 dose level.

Table 3.2 Eribulin Peripheral Neuropathy Dose Modification

Peripheral Neuropathy	Management/Next Dose for Eribulin
≤ Grade 1	No dose modification
Grade 2	For intolerable (as determined by physician and participant) grade 2, decrease eribulin by one dose level.
Grade 3	Hold eribulin until recovery to grade < 2 then reduce by 1 dose level.
Grade 4	Permanently discontinue eribulin.

Table 3.3 Eribulin Neutropenia Dose Modification

Neutropenia	Management/Next Dose for Eribulin
ANC < 500 cells/mm ³ lasting > 7 days with or without use of growth factors	Hold eribulin until recovery to grade < 2 and reduce by 1 dose level. Prophylactic growth factor support should be instituted for subsequent cycles.
ANC < 500 cells/mm ³ lasting ≤ 7 days without use of growth factors	Hold eribulin until recovery to grade < 2. Resume eribulin at the same dose. Growth factor support should be provided.
ANC < 500 cells/mm ³ lasting ≤ 7 days in despite use of growth factors	Hold eribulin until recovery to grade < 2, and reduce by 1 dose level. Continue ongoing prophylactic growth factor support for subsequent cycles.
ANC < 1000 /mm ³ with fever or infection without use of growth factors	Hold eribulin until recovery to grade < 2. Resume eribulin at the same dose. Growth factor support should be provided.
ANC < 1000 /mm ³ with fever or infection despite use of growth factors	Hold eribulin until recovery to grade < 2, and reduce by 1 dose level. Growth factor support should be provided.
ANC < 1000 /mm ³ without fever or infection	First occurrence: Hold eribulin until recovery to grade < 2 then resume at the same dose. Growth factor support should be provided. If uncomplicated neutropenia (<1000 /mm ³ without fever or infection) occurs/recurs despite growth factor support, then hold eribulin until recovery to grade < 2. Eribulin may be then be resumed at the same dose with growth factor support, or it may be reduced by one dose level. If a participant misses two consecutive Day 8 eribulin doses due to uncomplicated neutropenia, then hold eribulin until

Neutropenia	Management/Next Dose for Eribulin
	recovery to grade < 2, reduce by 1 dose level, and consider prophylactic growth factor support for subsequent cycles.
ANC = absolute neutrophil count	

Table 3.4 Eribulin Thrombocytopenia Dose Modification

Thrombocytopenia	Management/Next Dose for Eribulin

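### Section 5.5 ends all protocol therapy in situations where Section 6 resumes or stops a single agent, and the Section 5.6 scan interval after stopping can miss the week-12 assessment that decides the primary endpoint

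*Combined protocol and SAP*

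**What the plan says.** **Section 5.5** lists criteria for ending treatment and closes with "Participants will be removed from the protocol therapy when any of these criteria apply". Three of them matter here:

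- Grade 4 toxicity: "Any grade 4 events except as noted above". One exception covers drug-related laboratory or electrolyte abnormalities, limited to an abnormality "that does not require treatment except for electrolyte replacements".
- Repeat delays: "Participants requiring > two dose delays for the same type of event should be removed from protocol".
- Further immunosuppression: "Any participants who require additional immune suppressive treatment beyond steroids should go off study treatment".

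**Section 6** treats the same situations agent by agent. Its opening text says "For toxicities in this Section which are attributable to eribulin alone, only eribulin should be held", with a matching sentence for pembrolizumab, and lets the other drug continue with PI approval. For Grade 4 diarrhea, Table 3.1 says "Hold eribulin until recovery to grade < 2 then reduce by 1 dose level". Table 3.2 stops eribulin alone for Grade 4 neuropathy. The text after Table 4.9 stops pembrolizumab alone for repeat delays (not counting delays for evaluation) and for immunosuppression beyond steroids.

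**Scans.** Section 5.1 keeps restaging on schedule when treatment is delayed. Section 5.6 asks for scans every 8 weeks or 2 months, if possible, in participants who come off trial for a reason other than progression. Section 11.1 sets re-evaluation every 6 weeks (+/- 3 days) and does not limit it to time on treatment. Section 13.1 counts participants without the 12-week scan as failures, and Section 13.9.2 makes the analysis intent-to-treat.

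**The concern.** There are two linked problems.

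The first is clinical. Two investigators with the same patient could each follow the protocol and act differently: one ends both drugs, the other continues one or resumes at a lower dose.

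The second concerns the endpoint. A participant taken off therapy for toxicity before week 12, without progression, may move to a scan schedule that does not include week 12. Section 13.1 would then record a failure for a scheduling reason, and the participant stays in the denominator of 19. The decision rule needs 9 of 19 in each arm, so a few such cases matter.

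**Working it through.** **1. The instructions side by side**

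| Situation | Section 5.5 | Section 6 | Does any text rank them? |
|---|---|---|---|
| Grade 4 diarrhea | Off all protocol therapy | Table 3.1: hold eribulin, resume one level lower | No |
| Grade 4 neuropathy | Off all protocol therapy | Table 3.2: stop eribulin only | No |
| More than two delays, same type of event | Off protocol | Stop pembrolizumab only; evaluation delays exempt | No |
| Immunosuppression beyond steroids | Off study treatment | Stop pembrolizumab only | No |
| Expected eribulin-related hematologic events | Off if Grade 4 and needing more than electrolytes | Tables 3.3 to 3.5: hold and resume | Partly: a note after Table 4.2 sends these to the eribulin tables; 5.5 does not mention it |

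**2. Where the 5.6 scans fall.** Section 5.6 does not say from when the 8 weeks are counted. Taking the +/- 3 days from 11.1, the window is 12 weeks +/- 3/7 week, or weeks 11.57 to 12.43.

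- From baseline: weeks 8 and 16. Both miss.
- From the week-6 scan: 6 + 8 = week 14. Misses.
- From removal: inside the window only if removal falls between 11.57 - 8 = 3.57 and 12.43 - 8 = 4.43 weeks.

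**3. The plan's own power.** Inputs from Section 13.2: n = 19 per arm, success if at least 9 are progression-free, null 30%, alternative 60%. By exact binomial, P(Bin(19, 0.60) >= 9) = 0.912, which reproduces the stated 91%. P(Bin(19, 0.30) >= 9) = 0.084, within the 10% limit.

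**4. Effect of missing scans.** Let k of the 19 be scored as failures for want of the scan. The documents do not give k. Two cases:

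- The k are a random draw, so some would have failed anyway: power = P(Bin(19 - k, 0.60) >= 9), and type I error = P(Bin(19 - k, 0.30) >= 9).
- All k were otherwise progression-free: power = P(Bin(19, 0.60) >= 9 + k).

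| k | Power, random k | Type I error, random k | Power, all k otherwise progression-free |
|---|---|---|---|
| 0 | 91.2% | 8.4% | 91.2% |
| 1 | 86.5% | 6.0% | 81.4% |
| 2 | 80.1% | 4.0% | 66.7% |
| 3 | 71.6% | 2.6% | 48.8% |

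Power and type I error fall together, so the risk is missing an active regimen.

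**The case against.** **Much of the Grade 4 conflict is already handled.** A reader might infer that 5.5 ends both drugs for Grade 4 neutropenia, the most familiar eribulin toxicity. The documents do not support that as the plain result. The note after Table 4.2 sends expected eribulin-related hematologic events to the eribulin tables without delaying pembrolizumab, and Table 3.3 says, for a short first episode of ANC below 500, "Resume eribulin at the same dose. Growth factor support should be provided". Sections 5.1 and 5.8 also point to Section 6 for dose modification and toxicity management, and 5.3.3 and 5.3.4 allow one agent to continue. This stands. It shows the likely intent, but it is not a ranking rule, and it leaves the first four rows of the table open.

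**The scan may not be lost.** Section 11.1 can be read as keeping 6-weekly scans after treatment stops. Section 5.6 speaks of coming off trial, which need not mean stopping therapy. Section 13.1 gives no window, so a lenient reader might accept a later scan. The body of the study calendar (Table 7) is not in the text available here and might settle the matter. Calendar note j does not help the concern: it describes the schedule after Cycle 4, which is after week 12 (4 x 21 days = 84 days). All this stands, so the loss is a possibility under one of two readings.

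**The size cannot be read from the cited toxicity rates.** A reader might take the 18.7% rate of Grade 4 treatment-related events in Section 2.6 (19 x 0.187 = 3.6 per arm), or the 32% Grade 4 neutropenia in Section 2.5.2.5 (19 x 0.32 = 6.1), as the number of lost scans. Neither supports that. The first comes from a breast cancer trial, covers all event types with no week-12 limit, and may include laboratory events that 5.5 exempts. The second is the hematologic event already sent to the eribulin tables. Neither says who would lose a scan.

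**Conclusion.** The point holds in limited form. Sections 5.5 and 6 contradict each other for Grade 4 diarrhea, Grade 4 neuropathy, repeat delays and immunosuppression beyond steroids, and no visible text says which governs. For expected eribulin-related hematologic events the protocol already points to the eribulin tables, and 5.5 merely fails to say so.

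Separately, 5.6 and 11.1 leave unclear whether a participant who stops early without progression is scanned at week 12. If 5.6 applies, the scan is usually missed and 13.1, as worded, records a failure. The result would be a downward-biased week-12 rate and reduced power, with type I error moving down as well.

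The power losses in the working are illustrations. They rest on an assumed k of one to three per arm, on the 5.6 reading of the schedule, on the +/- 3-day window borrowed from 11.1, and on 13.1 being applied as written.

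**What to change.** 1. **Section 5.6**, add: *Participants who stop protocol therapy without progression keep the 6-weekly scans (+/- 3 days) through week 12, then move to every 8 weeks.*
2. **Section 5.5**, add: *Where Section 6 gives a specific instruction for a Grade 4 event, repeated dose delays or immune suppressive treatment beyond steroids, Section 6 governs, including its instructions to stop all study drug or go off study (Tables 4.7 and 4.8). The investigator's substantial-risk stop still applies.*

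The second sentence should not go on to say that only the agent blamed for the toxicity is held or stopped. That would collide with Table 4.2, whose Grade 4 row stops pembrolizumab even for unrelated events, with Table 4.7, which takes listed neurologic events off study, and with Table 4.8, which ends study drug after a Grade 3 or 4 infusion reaction.

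The cost is two sentences and at most one rescheduled scan per participant who stops early. The second change prefers the less restrictive section, which is a clinical decision, so the sponsor must confirm that the Section 6 instructions are the intended ones. The first change can be made whatever the answer.
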